## **5.0 Reporting of Adverse Events or Unanticipated Problems involving Risk to Participants or Others**

Adverse events, other than those measured as end points, should be reported to the principal investigator, [name] at **[contact]**.

## **6.0 Study Withdrawal/Discontinuation**

Participants may withdraw at any time before the procedure, and parents will have the ability to request that their child's data be withdrawn at any time prior to data analysis.

## **7.0 Statistical Considerations**

The primary outcome of the study will be desaturation below 80%. Resident training level, staff intervention required, number of intubation attempts and any adverse events will also be recorded. Our hypothesis is a significantly smaller percentage of patients in the CMAC group will desaturate below 80% compared to the DL group. A two group chi-square test with a 0.05 two-sided significance level will have 80% power to detect the difference between 30% vs. 5% proportion of O2sat dropping below 80% (odds ratio of 0.123) when the sample size in each group is 36.

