## **1.0 Background**

Infantile hypertrophic pyloric stenosis is a condition caused by marked hypertrophy and hyperplasia of the muscular layers of the pylorus. Pyloric stenosis occurs in approximately 1 out of every 300 live births in the United States. The highest incidence is in first born male children, specifically those who had an affected parent. The age of presentation ranges from 3 to 12 weeks, with 95% presenting at 8 weeks. Infants exhibit symptoms of non-bilious, projectile vomiting shortly after feeding. Pyloric stenosis can mimic failure to thrive and results in a hypochloremic, hyponatremic, metabolic alkalosis, and in severe cases of dehydration, metabolic acidosis. Treatment requires surgical pyloromyotomy.

During induction of anesthesia for the surgical pyloromyotomy, direct laryngoscopy is the primary method for securing an airway in the operating room. Any infant with the diagnosis of pyloric stenosis is considered to be at risk for aspiration of gastric contents, and therefore, requires a rapid sequence intubation for securing the airway. Rapid sequence intubation is challenging in infants and leads to frequent oxygen desaturation, perhaps even more frequent at a teaching institution, where resident anesthesiologists are securing the airway. With the introduction of the video laryngoscope, the staff anesthesiologist is able to have direct vision as the resident anesthesiologist secures the airway. This allows for early advice and intervention by the staff anesthesiologist. We hypothesize that the video laryngoscope will have a decreased incidence of oxygen desaturation when compared to conventional laryngoscopy in this patient population.

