#### **4.0 Study Procedures**

1. **Study design:** The study will be randomized, controlled, and prospective in design.
2. **Comparison groups** The two comparison groups will be:
  - a. **Conventional Laryngoscopy (DL), N = 35**  
Endotracheal intubation will be performed by conventional direct laryngoscopy.
  - b. **Video Laryngoscopy (CMAC), N = 37**  
Endotracheal intubation will be performed by video laryngoscopy with the C-MAC.
3. **Study and timeline of interventions**
  - a. **Preoperative:** All patients enrolled in this study will receive an intravenous catheter preoperatively.
  - b. **Intraoperative:** Subjects will all undergo induction of anesthesia by rapid sequence intubation. Upon arrival to the operating room, a new pulse oximeter probe will be placed on the patient's big toe. Orogastic suctioning with a 10 French Salem sump will be done with the patient supine, right and left lateral positions. Preoxygenation with 100% oxygen will be undertaken for approximately one minute. After pre-oxygenation, a rapid sequence induction will occur with Propofol 2.5mg/kg and Succinylcholine 2.5mg/kg IV. The resident will two-hand mask the patient and the staff anesthesiologist will manually ventilate the patient maintaining airway pressures less than 15mmHG. Approximately twenty seconds after administration of succinylcholine, direct laryngoscopy with a Miller 1 blade or a CMAC 0 blade will be undertaken. The patient will be intubated with a 3.0 cuffed endotracheal tube that has been loaded with a stylet. If the resident is having difficulty securing the airway, the staff may intervene at any point. The airway will be deemed secure when end tidal CO2 x 3 is seen, chest rise is adequate, and bilateral and equal breath sounds are heard. Anesthesia will be maintained with sevoflurane. The patient will be extubated at the conclusion of the case when he/she meets extubation criteria.
  - c. **Postoperative:** All patients will receive routine PACU care. Pain and anxiety scores will be recorded according to routine PACU practice. Medication for pain, nausea, and anxiety will be given according to the judgment of the anesthesiologist.
  - d. **Measured end-points:**
    - i. Level of resident training
    - ii. Desaturation below 80% during induction

- iii. Staff intervention needed for intubation
- iv. Number of intubation attempts

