## **9.0 Follow-up and Record Retention**

The participation in the study begins with induction of anesthesia, and ends when the patient is discharged from recovery room. There will be no patient follow-up after the day of the procedure.

The patient data related to the study will be entered into a secure REDCap database. Paper copies of study data will be kept in the locked anesthesiology offices. Following completion of the study, all copies of data collected will be stored for the required amount of time (min. 7 years) and then will be physically destroyed.

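### Does the missing start and end time for the primary desaturation outcome leave the comparison or the stated 80% power unsound?

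*Combined protocol and SAP*

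**What the plan says.** Section 7.0 Statistical Considerations names the outcome: "The primary outcome of the study will be desaturation below 80"%. It gives no start or end, and the power sentence (30% versus 5%, two-sided chi-square test at 0.05, 36 per group, 80% power) gives none either. The list of measured end-points in 4.0 Study Procedures, item 3d, has the same event with a period attached: "Desaturation below 80% during induction".

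Induction is used in two ways. The wide use is in 1.0 Background, "During induction of anesthesia for the surgical pyloromyotomy, direct laryngoscopy is the primary method for securing an airway in the operating room", and in 4.0 item 3b, "Subjects will all undergo induction of anesthesia by rapid sequence intubation". The narrow use, also in item 3b, is the drug step: "After pre-oxygenation, a rapid sequence induction will occur with Propofol 2.5mg/kg and Succinylcholine 2.5mg/kg IV". Item 3b goes on to define a secure airway ("The airway will be deemed secure when end tidal CO 2 x 3 is seen, chest rise is adequate, and bilateral and equal breath sounds" heard) but does not tie that moment to the end-point. Section 9.0 Follow-up and Record Retention sets the length of participation: "The participation in the study begins with induction of anesthesia, and ends when the patient is discharged from recovery room".

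**The concern.** The trial has one primary outcome, and its window is not written out in the section that carries the power claim. Three readings seem open:

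- **Widest:** any fall below 80% up to recovery-room discharge counts. Events unrelated to the laryngoscope would then enter both arms and dilute the difference.
- **Narrowest:** only the drug step counts. The window would close before the two arms differ.
- **Middle:** induction through intubation. A low value appearing on the toe probe just after the tube is placed might or might not count.

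The operators know which device they are using, and the list of end-points holds only the yes/no event and not the lowest saturation. A loose boundary could therefore cost power or let in judgement, and another window could not be rebuilt later from the listed end-points.

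**Working it through.** **1. The plan's own figure.** Inputs from section 7.0: p1 = 0.30 (conventional), p2 = 0.05 (video), n = 36 per arm, two-sided 0.05. With mean proportion p̄ = 0.175:

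- Required n = [1.960·√(2·0.175·0.825) + 0.842·√(0.30·0.70 + 0.05·0.95)]² / 0.25² = (1.053 + 0.427)² / 0.0625 = 35.1, rounded up to 36.
- Power at 36 = Φ[(0.25·√36 − 1.053) / √0.2575] = Φ(0.447 / 0.507) = Φ(0.88) = 81%.
- Exact enumeration of the uncorrected chi-square test gives 85%.
- Odds ratio = (0.05/0.95) / (0.30/0.70) = 0.123, as stated.

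The figure is right for 30% versus 5%. It changes only if the rates in the analysed window differ from these, and the documents do not say that they do.

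**2. The three readings against the text.**

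- *Recovery room included.* This comes from section 9.0, which sets how long a child is in the study and does not mention the outcome. The end-point list restricts the event to induction. Adverse events other than end-points have their own reporting route in the adverse-event section, and 7.0 records adverse events separately.
- *Drug step only.* Section 2.0 asks whether desaturation differs between two intubation techniques, and the Background attributes desaturation to rapid sequence intubation. A window ending before laryngoscopy would measure neither. Both wide uses of the word put laryngoscopy inside induction.
- *Induction through intubation.* This fits 1.0, 2.0, 4.0 and 7.0 together. Only the exact closing moment is unstated.

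**3. How large the losses would be on assumed rates** (36 per arm, exact chi-square).

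Added background events at rate q in both arms, p = 1 − (1 − p0)(1 − q):

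| q (assumed) | Conventional | Video | Power |
|---|---|---|---|
| 0 | 30% | 5% | 85% |
| 2% | 31.4% | 6.9% | 79% |
| 5% | 33.5% | 9.75% | 71% |
| 10% | 37.0% | 14.5% | 60% |

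A fifth of events lost in both arms: 0.8 × 30% = 24% and 0.8 × 5% = 4%, power 75%.

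The two scenarios need opposite premises. Dilution requires 30% and 5% to describe the short window, while loss requires them to describe a longer one. The documents support neither, and dilution also needs the recovery-room reading rejected in step 2.

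**4. Lowest saturation as a secondary outcome.** If saturation were roughly normal with equal spread, 30% versus 5% would be a shift of 1.645 − 0.524 = 1.12 SD, and a t-test at 36 per arm would have 99.7% power. That gain comes from the assumed shape. If the device changes only the share of infants falling below 80% and leaves the rest of the distribution alike, simulation gives about 45% power for a rank test against 85% for the chi-square test. Either way, the primary result is untouched.

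**The case for a change.** The best case for a change is that even the sensible reading has no stated end: passage of the tube, the three carbon dioxide readings, or some time later. If the toe probe lags, falls caused by laryngoscopy may be displayed just at that boundary. The loss need not be equal: if only the conventional arm lost a fifth of its events (24% versus 5%), exact power would be 68%; if only the video arm did (30% versus 4%), it would be 90%. Expected events are few, 36 × 0.30 = 10.8 and 36 × 0.05 = 1.8, and the operators are not blinded.

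It stands that the end is unstated and that a sentence naming it would be tidy. The harm is not shown. The documents give no probe delay and no time to intubation by arm, and nothing suggests that the window would be picked case by case. A number on a monitor crossing 80% leaves limited room for opinion.

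The result is also less fragile than the small counts suggest. With a and b events, X² = 72(a − b)² / [(a + b)(72 − a − b)], critical value 3.84. At 11 versus 2, X² = 72·81/(13·59) = 7.60. An earlier close would have to remove four conventional events and no video event to lose significance (8 versus 2 gives 4.18; 7 versus 2 gives 3.17). A later close would have to add three video events and no conventional event (11 versus 4 gives 4.13; 11 versus 5 gives 2.89). A boundary applied alike in both arms is unlikely to act so one-sidedly.

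**Conclusion.** No change is needed. Section 7.0 omits the window and 4.0 supplies it, so there are not two rival definitions. The documents' own usage and stated aim lead to one working reading: a saturation below 80% from induction through intubation. The same yes/no count and the same chi-square test follow wherever the window closes around airway confirmation. The stated 80% power is correct for its inputs (81% approximate, 85% exact). Losses down to 60–79% appear only under assumed event rates.

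This conclusion rests on two assumptions: that the team applies the same window in both arms, and that 30% and 5% were meant for that period. Both are the ordinary reading of the plan. Recording the lowest saturation is a matter of preference; it would not alter the primary comparison, and its benefit depends on how the device shifts the distribution.

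### Does it matter that Section 7.0 does not say whether the primary chi-square test is continuity-corrected?

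*Combined protocol and SAP*

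**What the plan says.** Section 7.0 (Statistical Considerations) is a single paragraph. It makes desaturation below 80% the primary outcome and states the hypothesis as "a significantly smaller percentage of patients in the CMAC group will desaturate below 80% compared to the DL group". The test follows directly: "A two group chi-square test with a 0.05 two-sided significance level will have 80% power", for a contrast of "30% vs. 5% proportion of O2sat dropping below 80% (odds ratio of 0.123) when the sample size in each group is 36".

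No other section names a test. The documents do not mention a continuity correction, Fisher's test or any other exact test. The Enrollment/Randomization section also gives 36 per group. Study Procedures gives "Conventional Laryngoscopy (DL), N = 35" and "Video Laryngoscopy (CMAC), N = 37", which has the same total of 72.

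**The concern.** Two different statistics are commonly called a chi-square test: Pearson's, and the version with Yates's continuity correction. With about 36 infants per arm and about two events expected under video laryngoscopy (36 × 0.05 = 1.8), they can fall on opposite sides of 0.05. With 8 events against 2 at 36 per arm, for example, Pearson gives p = 0.041 and the corrected test p = 0.088.

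The test appears only in a power statement, and strictly that describes a planning assumption. If the version were really open, an analyst could choose it after seeing the counts and so settle the primary conclusion without departing from the written plan. The stated 80% power would also hold for only one of the two versions.

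**Working it through.** **Inputs.** All are from Section 7.0: p₁ = 0.30 (conventional laryngoscopy), p₂ = 0.05 (video laryngoscopy), two-sided α = 0.05 (z = 1.960), power 80% (z = 0.8416), 36 per group. The stated hypothesis determines which rate belongs to which arm. The 35/37 split is from Study Procedures.

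**1. Reproduce the plan's figures.** Odds ratio: (0.05/0.95)/(0.30/0.70) = 0.1228, stated as 0.123.

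Uncorrected sample size, with p̄ = 0.175:

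n = [1.960·√(2·0.175·0.825) + 0.8416·√(0.30·0.70 + 0.05·0.95)]² / 0.25²
= [1.0532 + 0.4271]² / 0.0625 = 35.06, so **36 per group**.

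Continuity-corrected sample size:

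n′ = (n/4)·[1 + √(1 + 4/(n·0.25))]² = 8.765·[1 + 1.2068]² = 42.7, so **43 per group**.

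Normal-approximation power at 36 per group is 81.1% uncorrected and 71.0% corrected.

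**2. Which version fits the text?**

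| Version | n per group for 80% power |
|---|---|
| Two-sided, uncorrected | 36 |
| Two-sided, corrected | 43 |
| One-sided, uncorrected | 28 |
| One-sided, corrected | 36 |

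The last row also gives 36, but the text says two-sided. Only the uncorrected two-sided test fits every stated input.

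**3. Is that version sound here?** At the average design rate the expected number of events is 36 × 0.175 = 6.3 per arm, above the usual threshold of 5. Full binomial enumeration gives exact power of 85.1% at 36/36 and 85.2% at 35/37. The maximum exact size is 5.8% at 36/36 (common rate near 10%) and 5.05% at 35/37. At a common rate of 17.5% and 36/36 it is 5.06%.

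**4. How often would the two versions disagree?** The corrected p-value is never smaller than the uncorrected one, so the difference in exact power is the probability of disagreement at the design rates.

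| Group sizes (conventional/video) | Pearson power | Corrected power, every table | Disagreement |
|---|---|---|---|
| 36/36 | 0.8508 | 0.7591 | 9.2% |
| 35/37 | 0.8518 | 0.7276 | 12.4% |
| 37/35 | 0.8328 | 0.7508 | 8.2% |

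These figures assume that the analyst corrects every table. If the correction is used only when an expected count is below 5, power is 0.8205 at 36/36 and 0.7892 at 35/37. Disagreement with Pearson is then 0.8508 − 0.8205 = 3.0% and 0.8518 − 0.7892 = 6.3%. Switching to Fisher's test on the same rule gives 3.0% at 36/36 and 0.8518 − 0.8397 = 1.2% at 35/37.

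Two of the likeliest disagreeing tables at 36/36 are 8 vs 2 and 10 vs 3. Their smallest expected counts are 10/2 = 5.0 and 13/2 = 6.5, so that rule would keep Pearson for both.

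With equal rates in the two arms (values from 5% to 30% were checked), disagreement even with every table corrected is 2.4% to 4.4%. It is 2.6% at 17.5% and 36/36.

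The table nearest the design expectation (10.8 and 1.8 events at 36/36) is 11 vs 2. It is significant either way: p = 0.006 uncorrected and 0.014 corrected.

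**The case for a change.** The best case for the concern is that a sample-size basis is not an analysis commitment. A reader has to work backwards from 36 to find the version, and an analyst who applied the correction could still say that a chi-square test had been done. The every-table figures use the plan's own rates and group sizes, and they reproduce. The corrected test would also fall short of 80% at either set of group sizes: exact power is 75.9% at 36/36 and 72.8% at 35/37.

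What stands is narrow. No sentence says that the test is uncorrected, and adding one would cost nothing. But that sentence would only repeat what the sample size already implies. It would leave the sample size, the data collection, the stated power and the result of following the plan as they are. The larger figure, 12.4%, also depends on the 35/37 allocation. How that fits with 36 per group elsewhere is a separate question, and reversing the two sizes brings the figure down to 8.2%.

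**Conclusion.** The concern does not hold. Section 7.0 puts one unqualified chi-square test directly after one binary primary outcome and one two-group hypothesis. Its 36 per group at two-sided 0.05 and 80% power matches the uncorrected Pearson test and not the corrected one, which needs 43. Nothing in the documents points to a correction or to an exact test. Used as the plan implies, the Pearson test has 85.1% exact power at 36/36, and its exact size is never above 5.8%.

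The 9.2% to 12.4% disagreement describes a departure from the plan's sizing basis on every table. It is not a property of the plan as written. It is also the probability that two fixed tests differ, not the probability that this trial's conclusion would turn on a later choice. This conclusion assumes the stated rates of 30% and 5%, independent binomial counts, and the two-sided level given in the text.

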## **8.0 Privacy/Confidentiality Issues**

Participant privacy is an important goal of the researchers. Only members of the research team will have access to identifiable data. Data will be stored in a secure REDCap database. Only members of the research team will have access to REDCap data. Paper copies of PHI will be kept with study charts and paperwork in the locked anesthesiology offices until data analysis is completed and the paperwork is no longer needed, or for 7 years per Indiana law.

## **9.0 Follow-up and Record Retention**

The participation in the study begins with induction of anesthesia, and ends when the patient is discharged from recovery room. There will be no patient follow-up after the day of the procedure.

The patient data related to the study will be entered into a secure REDCap database. Paper copies of study data will be kept in the locked anesthesiology offices. Following completion of the study, all copies of data collected will be stored for the required amount of time (min. 7 years) and then will be physically destroyed.
